3.6.1 Titration of IDegAsp BID

The breakfast/lunch dose adjustment will be based on the three pre-dinner SMPG values measured on three days prior to the titration in accordance with [Table 6](#) and [Table 7](#).

The dinner dose adjustment will be based on the mean of three pre-breakfast SMPG values measured on the day of titration and the two days prior to the titration in accordance with [Table 6](#) and [Table 7](#).

Table 6 Increase of IDegAsp BID

Mean pre-breakfast or pre-dinner SMPG		Dose adjustment
mmol/L	mg/dL	U
4.0 – 5.0	71 – 90	No adjustment
5.1 – 7.0	91 – 126	+2
7.1 – 8.0	127 – 144	+4
8.1 – 9.0	145 – 162	+6
> 9.0	> 162	+8

If one or more SMPG values are missing, the dose adjustment should be performed on the remaining SMPG value(s).

Table 7 Dose reduction of IDegAsp BID

Lowest pre-breakfast or pre-dinner SMPG		Dose adjustment
mmol/L	mg/dL	U
3.1 – 3.9	56 – 70	-2
< 3.1	< 56	-4

3.6.2 Titration of IAsp

If HbA_{1c} at week 26 is <7.0%, the subject should continue on IAsp OD and titration according to [Table 5](#).

If HbA_{1c} at week 26 is ≥ 7.0% IAsp treatment should be intensified with a second dose of IAsp. The second dose should be initiated at 4U. Titration should be performed according to [Table 5](#).

If HbA_{1c} at week 32 is ≥ 7% IAsp treatment should be intensified with an additional dose of IAsp initiated at 4U. Titration should be performed according to [Table 5](#).

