5.3.3 Trial insulin treatment

Subjects will receive either IDegAsp OD or IGlar OD + IAAsp OD during the first 26 weeks and continue into a 12-week intensification period.

Subjects on a pre-trial BID/TID basal insulin regimen will be shifted to OD dosing in accordance with the Titration Guideline, [Appendix A](#).

For information about initial doses, area of injection, dosing time and the weekly dose adjustments during the initial treatment period (week 2-26), refer to the Titration Guideline, [Appendix A](#).

At week 26 (V28), subjects not achieving sufficient glycaemic control ($V27 \text{ HbA}_{1c} \geq 7\%$) will be further intensified from either IDegAsp OD to IDegAsp BID or IGlar OD + IAAsp OD to IGlar OD + IAAsp BID. Subjects in good glycaemic control ($V27 \text{ HbA}_{1c} < 7\%$) will continue their insulin treatment regimen.

At week 32 (V34), glycaemic control will be evaluated again, and subjects in good glycaemic control ($V33 \text{ HbA}_{1c} < 7\%$) will continue their insulin treatment regimen. Subjects on IDegAsp OD not reaching the glycaemic target ($V33 \text{ HbA}_{1c} \geq 7\%$) will be intensified to IDegAsp BID, whereas subjects in the IGlar arm not reaching glycaemic control will be intensified with one additional IAAsp dose to IGlar OD + IAAsp BID or TID daily for the remaining six weeks of the intensification period.

Information about doses, dosing time and dose adjustments during the treatment intensification period (week 27-38) can be found in the Titration Guideline, [Appendix A](#).

Information about insulin treatment in the ‘washout’ period between the EOT visit (V40) and the 7-day follow-up visit (V41) can be found in Section [5.5](#).

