3.6 Treatment after week 26 of IDegAsp and IA_{Sp}

If HbA_{1c} taken at week 25 is <7.0%, the subject should be titrated at week 26 according to [Table 3](#) and [Table 4](#).

If HbA_{1c} taken at week 25 is ≥ 7.0% IDegAsp treatment should be intensified to BID at week 26 as described below.

At week 32 subjects still on IDegAsp OD should be intensified to BID if HbA_{1c} taken at week 31 is ≥ 7.0%.

Intensification from IDegAsp OD to BID should be done by splitting the total daily dose of IDegAsp OD into two doses of IDegAsp. The split can be even or uneven as based on the size of the meals. Subjects with HbA_{1c} < 7.0% measured at week 25 or 31 can be switched to IDegAsp BID at weeks 26 or 32 at the discretion of the investigator based on the needs of the individual subject.

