Subjects will remain in the same treatment arm throughout the trial, with the possibility of intensification of their treatment. At week 26 (V28), subjects not achieving sufficient glycaemic control (V27 HbA_{1c} ≥ 7%) will be further intensified from either IDegAsp OD to IDegAsp BID or IGlar OD + IAsp OD to IGlar OD + IAsp BID, whereas subjects in good glycaemic control (V27 HbA_{1c} < 7%) will continue their insulin treatment regimen.

At week 32 (V34), glycaemic control will be evaluated again, and subjects in good glycaemic control (V33 HbA_{1c} < 7%) will continue their insulin treatment regimen. Subjects on IDegAsp OD not reaching the glycaemic target (V33 HbA_{1c} ≥ 7%) will be intensified to IDegAsp BID, whereas subjects in the IGlar arm not reaching glycaemic control will be intensified with one additional IAsp dose to IGlar OD + IAsp BID or TID daily for the remaining six weeks of the intensification period.

Further details

For further details on trial design and endpoints please see the NN5401-4266 protocol version 4.0.

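### Appendix A 3.6.2 names a different HbA1c sample for stepping up insulin aspart than the rest of the protocol and the SAP, so comparator subjects could be intensified on another sample

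*Protocol*

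**What the plan says.** The protocol body and the SAP give one trigger for both arms. SAP 1.1 states that "subjects not achieving sufficient glycaemic control (V27 HbA_{1c} ≥ 7%) will be further intensified", with the change made at V28. For the second evaluation, at V34, it states that "subjects in good glycaemic control (V33 HbA_{1c} < 7%) will continue their insulin treatment regimen". Protocol sections 1 and 5.3.3 say the same.

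Appendix A, the titration guideline, treats the two products separately.

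- **IDegAsp, section 3.6.** First step: "If HbA_{1c} taken at week 25 is ≥ 7.0% IDegAsp treatment should be intensified to BID at week 26 as described below". Second step: "At week 32 subjects still on IDegAsp OD should be intensified to BID if HbA_{1c} taken at week 31 is ≥ 7.0" (per cent).
- **IAsp, section 3.6.2.** First step: "If HbA_{1c} at week 26 is ≥ 7.0% IAsp treatment should be intensified with a second dose of IAsp". Second step: "If HbA_{1c} at week 32 is ≥ 7% IAsp treatment should be intensified with an additional dose of IAsp initiated at 4U".

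Section 2.17 of global amendment 1 rewords the second IAsp step to make it subject to the investigator's judgement. It leaves the reference to HbA1c at week 32 as it was.

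**The concern.** Protocol 5.3.3 sends sites to Appendix A for doses, dosing times and dose adjustments in weeks 27 to 38, so 3.6.2 is text that sites will have in hand when managing comparator subjects. Read literally, it names a sample one week later than the one named for IDegAsp. The week-26 reference is not an empty one: Protocol 17.4 uses a separate HbA1c value from V28 as the primary-endpoint measurement. HbA1c is a central-laboratory assay (Protocol 8.5.1), so a result from blood drawn at V28 may not be available when the V28 dosing decision is made.

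The second secondary objective compares the two stepwise regimens at 38 weeks. Change in HbA1c, the HbA1c responder rate below 7%, severe or BG confirmed symptomatic hypoglycaemia and TEAEs over 38 weeks are all marked in Protocol 4.2.2 as key endpoints for disclosure. SAP 3.6 adds TEAEs in weeks 26 to 38. The trial is open-label, so the staff applying an arm-specific rule know the arm. If the decision sample differed by arm, part of any week-38 difference could come from how the intensification rule was applied and not from the regimens.

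**Working it through.** No stated figure of the plan is at issue. The check sets the texts side by side and maps visits to weeks.

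**Step 1. Visit weeks.** From the flow chart (Protocol Table 2-1): V27 = week 25, V28 = week 26, V33 = week 31, V34 = week 32, V40 = week 38. The gaps are 26 − 25 = 1 week and 32 − 31 = 1 week.

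**Step 2. The rules compared.**

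| Source | Arm | First-step HbA1c | Second-step HbA1c | When the change is made |
|---|---|---|---|---|
| Protocol 1 and 5.3.3 | Both | V27 (week 25) | V33 (week 31) | V28, V34 |
| SAP 1.1 | Both | V27 (week 25) | V33 (week 31) | V28, V34 |
| Appendix A 3.6 | IDegAsp | Week 25 | Week 31 | Weeks 26, 32 |
| Appendix A 3.6.2 | IAsp | Week 26 | Week 32 | Not stated |
| Amendment 1, section 2.17 | IAsp | Not addressed | Week 32 | Not stated |
| Appendix A 2.2 | Both | None named | None named | Week 26 in both arms; week 32 for the third IAsp dose |

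Section 3.6.2 and its amended sentence are the only texts that name weeks 26 and 32 for the sample. The week-26 reference appears twice in 3.6.2, once for each side of the 7.0% threshold, and the week-32 reference once.

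**Step 3. Does the later sample exist?** At V28 it does (Protocol 17.4). At V34 this cannot be confirmed from the text available, because the HbA1c rows of the flow chart did not survive extraction. That gap is not a fault of the plan.

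**Step 4. What a delay would cost, if there were one.** Planned time after the first step is 38 − 26 = 12 weeks, and after the second 38 − 32 = 6 weeks. The documents give no turnaround time, so the delay d is an assumption. Remaining time is 12 − d and 6 − d; the share lost is d/12 and d/6.

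| Assumed delay d (weeks) | Left after first step | Left after second step |
|---|---|---|
| 0 | 12 (0% lost) | 6 (0% lost) |
| 1 | 11 (8% lost) | 5 (17% lost) |
| 2 | 10 (17% lost) | 4 (33% lost) |

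**Step 5. Which endpoints can be reached.** Under every reading the first intensification comes at V28 or later. The week-26 HbA1c, on which the only formal hypothesis test rests, is therefore untouched. Only the 38-week and intensification-period outcomes are exposed.

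**The case against.** The strongest reply is that the protocol already settles the trigger. Section 5.3.3 states it outright for both arms and refers to Appendix A for doses and their adjustment, so a site would have to set the body aside to follow 3.6.2 literally. Section 3.6.2 does not say when the blood was taken, and its week numbers may be loose wording for the decision visit. The practical difficulty of using a V28 result at V28 supports that looser reading. Contacts are weekly, the sponsor reviews titration data within 24 hours on weekdays and monitors HbA1c, and the investigator may overrule the guideline. The amended second IAsp step is discretionary.

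Most of this stands, and it limits how far the point can go. Two stronger inferences are tempting and neither is supported.

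- **That the arms are in fact intensified at different times, to the advantage of IDegAsp on HbA1c.** No passage gives the comparator a later start. Protocol 5.3.3, SAP 1.1 and Appendix A 2.2 place the first change at week 26 in both arms. A later start needs an assumed laboratory delay, and no effect of such a delay on week-38 HbA1c can be estimated from the documents.
- **That samples one week apart would select different kinds of subject in the two arms.** A simulation assuming mean HbA1c of 7.0 to 7.3%, SD 0.8 to 1.0 and paired-difference SD 0.15 to 0.3 puts 4.5% to 11.6% of subjects on opposite sides of 7.0%. None of these inputs is in the documents. The model also treats the two samples as exchangeable, so the expected proportion intensified is the same whichever is used. The figure describes disagreement within a subject, not a difference between arms.

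The reply does not remove the contradiction. The looser reading has to be supplied by the reader, the neighbouring section for IDegAsp is explicit about when its sample is taken, and the amendment revisited the week-32 sentence without changing the reference.

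**Conclusion.** The inconsistency is established from the text: for IAsp, 3.6.2 names HbA1c at weeks 26 and 32, while Appendix A 3.6 names weeks 25 and 31 for IDegAsp and the protocol body and SAP name V27 and V33 for both arms. The consequence is conditional. If a site applies 3.6.2 literally, the comparator arm could be judged on a different sample, and if the result takes time to return, it could be intensified later. The second-step version also requires an HbA1c at V34, which is unconfirmed. The losses of 0 to 17% and 0 to 33% of intensified time illustrate assumed delays of 0 to 2 weeks; they are not estimates.

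The week-26 non-inferiority conclusion is not at risk. The possible effect is confined to week-38 and intensification-period HbA1c, responders, hypoglycaemia and TEAEs, with size and direction unknown. I rate this a moderate internal inconsistency: more than clerical, because it concerns an arm-specific treatment rule in an open-label comparison, but not a defect that must be cured before the primary result can be relied on.

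**What to change.** Reconcile Appendix A 3.6.2 (including its amended week-32 sentence), Appendix A 3.6, Protocol sections 1 and 5.3.3 and SAP 1.1. For each of the two steps they should state one consistent decision sample, identified by visit number, and one decision visit. If the agreed wording refers to a V34 sample, check that the flow chart schedules one. Then inform the sites. Which sample and rule are clinically right is for the sponsor and its medical advisers; no view is taken here.

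The cost is a wording change and a site memo. V27, V28 and V33 HbA1c are already part of the plan, so a rule based on those visits needs no extra blood draw. The primary analysis and the sample size do not change.

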3.7 Deviations from the algorithm

It is recommended that the algorithm is followed. However, it is also important that the decision to adjust the insulin doses is based on all relevant information as described in Section 1. A reason for deviating from the algorithm should be entered into the eCRF.

4 Data collection

The following data should be entered into the eCRF within 24 hours (on weekdays) after a site visit/phone contact:

- Per protocol SMPG values measured since last visit/telephone
- Date, time and doses of IDegAsp, IGlar and IAsp
- Prescribed doses of IDegAsp, IGlar and IAsp
- Reasons for deviation from the titration algorithms, if applicable
- Hypoglycaemic episodes

5 Review procedure

Surveillance of titration data will be performed centrally by Novo Nordisk in an unbiased manner. It is important that data regarding dose titration is entered into the eCRF within 24 hours (on weekdays). If delays occur, action cannot be taken in due time before the subject's next site visit/phone contact. The aim is to reduce the time periods in which a subject may receive suboptimal treatment.

The data listed in section [4](#) will be reviewed by Novo Nordisk within 24 hours (on weekdays). The reviewer may contact the investigator to get clarification regarding the reason for deviation or to request entry of missing data.

When the investigator receives an inquiry, a response should be received at Novo Nordisk within 24 hours (on weekdays).

During the trial HbA_{1c} will be monitored by Novo Nordisk for additional surveillance of the glycaemic control. Novo Nordisk may be in contact with sites (visit or phone contact) to discuss progress in glycaemic control and titration of individual subjects based on SMPGs and HbA_{1c}. This will be done in an unbiased and whenever possible blinded manner.

6 References

FPG	fasting plasma glucose
HbA _{1c}	glycosylated haemoglobin
IAsp	insulin aspart
ICH	International Conference on Harmonisation
IDeg	insulin degludec
IDegAsp	insulin degludec/insulin aspart
IGlar	insulin glargine
ITT	intention-to-treat
MMRM	mixed model for Repeated Measurement
NA	not applicable
NI	non-inferiority
OAD	oral antidiabetic drug
OD	once daily
PG	plasma glucose

PP	per protocol
REML	restricted maximum likelihood
SAP	statistical analysis plan
SD	standard deviation
SF-36v2®	Short-Form Health Survey 36 version 2
SMPG	self-measured plasma glucose
TEAE	treatment-emergent adverse event
TID	three times daily
TE	treatment effect
TRIM-D	Treatment Related Impact Measure-Diabetes
T2DM	type 2 diabetes mellitus

1 Introduction

1.1 Trial information

Objectives and endpoints

The primary objective

- To confirm the effect of insulin degludec/insulin aspart once daily versus insulin glargine once daily in combination with insulin aspart once daily in controlling glycaemia after 26 weeks in subjects with type 2 diabetes mellitus treated with basal insulin with or without oral antidiabetic treatment in need of treatment intensification.

The secondary objectives

- To compare other effect parameters and safety of insulin degludec/insulin aspart once daily versus insulin glargine once daily in combination with insulin aspart once daily after 26 weeks in subjects with type 2 diabetes mellitus treated with basal insulin with or without oral antidiabetic treatment in need of treatment intensification.
- To compare the effect and safety of insulin degludec/insulin aspart once daily or twice daily versus insulin glargine once daily in combination with insulin aspart (1-3 times daily) after 38 weeks in subjects with type 2 diabetes mellitus treated with basal insulin with or without oral antidiabetic treatment in need of treatment intensification.

Primary endpoint

- Change from baseline in glycosylated haemoglobin (HbA_{1c}) (%) after 26 weeks

Supportive secondary efficacy endpoints:

- Change from baseline in HbA_{1c}(%) after 38 weeks
- Change from baseline in fasting plasma glucose (FPG) after 26 weeks
- Change from baseline in fasting plasma glucose (FPG) after 38 weeks
- Responder (Yes/No) for HbA_{1c} after 26 weeks: HbA_{1c} < 7%
- Responder (Yes/No) for HbA_{1c} after 38 weeks: HbA_{1c} < 7%
- Responder (Yes/No) for HbA_{1c} after 26 weeks: HbA_{1c} < 7% without severe or BG confirmed symptomatic hypoglycaemia
- Responder (Yes/No) for HbA_{1c} after 38 weeks: HbA_{1c} < 7% without severe or BG confirmed symptomatic hypoglycaemia
- Self-measured plasma glucose measurements (SMPG) after 26 weeks: Mean pre-breakfast measurements used for titration

- Self-measured plasma glucose measurements (SMPG) after 38 weeks: Mean pre-breakfast measurements used for titration
- Self-measured plasma glucose measurements (SMPG) after 26 weeks: 9-point profile - Post-prandial increments
- Self-measured plasma glucose measurements (SMPG) after 38 weeks: 9-point profile - Post-prandial increments

Supportive secondary safety endpoints:

- Incidence of treatment-emergent adverse events (TEAEs) from baseline to week 26
- Incidence of treatment-emergent adverse events (TEAEs) during 38 weeks
- Incidence of treatment-emergent adverse events (TEAEs) during intensification period (week 26-38)
- Number of nocturnal, treatment-emergent severe or BG confirmed symptomatic hypoglycaemic episodes during 26 weeks
- Number of nocturnal, treatment emergent severe or BG confirmed symptomatic hypoglycaemic episodes during 38 weeks
- Number of nocturnal, treatment emergent severe or BG confirmed symptomatic hypoglycaemic episodes during maintenance (week 16-26)
- Number of treatment-emergent severe or blood glucose (BG) confirmed symptomatic hypoglycaemic episodes during 26 weeks
- Number of treatment-emergent severe or blood glucose (BG) confirmed symptomatic hypoglycaemic episodes during 38 weeks
- Number of treatment emergent severe or BG confirmed symptomatic hypoglycaemic episodes during maintenance (week 16-26)
- Total insulin dose at week 26
- Total insulin dose at week 38
- Change in weight from baseline to week 26
- Change in weight from baseline to week 38

Explorative endpoints

- Change from baseline to week 26 for:
 - Health-related quality of life as evaluated by SF-36v2® Health Survey
 - Treatment related impact as evaluated by the Treatment Related Impact Measure-Diabetes (TRIM-D)
- Change from baseline to week 38 for:
 - Health-related quality of life as evaluated by the SF-36v2® Health Survey

- Treatment related impact as evaluated by the TRIM-D

Trial design:

This is a 38-week, multinational, open-label, two-arm, randomised (1:1), controlled, parallel-group, treat-to-target trial in subjects with type 2 diabetes mellitus treated with basal insulin with or without oral antidiabetic drug(s) in need of treatment intensification. Subjects will be randomised in a 1:1 manner to receive either insulin degludec/insulin aspart (IDegAsp) OD or insulin glargine (IGlar) OD in combination with insulin aspart (IAsp) OD for the first 26 weeks followed by a 12-weeks intensification period. The randomisation will be stratified based on the pre-trial basal insulin treatment regimen: OD or BID/TID (two/three times daily) dosing.

Subjects will remain in the same treatment arm throughout the trial, with the possibility of intensification of their treatment. At week 26 (V28), subjects not achieving sufficient glycaemic control (V27 HbA_{1c} ≥ 7%) will be further intensified from either IDegAsp OD to IDegAsp BID or IGlar OD + IAsp OD to IGlar OD + IAsp BID, whereas subjects in good glycaemic control (V27 HbA_{1c} < 7%) will continue their insulin treatment regimen.

At week 32 (V34), glycaemic control will be evaluated again, and subjects in good glycaemic control (V33 HbA_{1c} < 7%) will continue their insulin treatment regimen. Subjects on IDegAsp OD not reaching the glycaemic target (V33 HbA_{1c} ≥ 7%) will be intensified to IDegAsp BID, whereas subjects in the IGlar arm not reaching glycaemic control will be intensified with one additional IAsp dose to IGlar OD + IAsp BID or TID daily for the remaining six weeks of the intensification period.

Further details

For further details on trial design and endpoints please see the NN5401-4266 protocol version 4.0.

1.2 Scope of the statistical analysis plan

This SAP is based on the NN5401-4266 protocol version 4.0.

2 Statistical considerations

Novo Nordisk will analyse and report data from all sites together.

Unless otherwise specified, all continuous measurements will be summarised descriptively at each visit by treatment using in-trial data. Endpoints that are analysed untransformed and endpoints that are not formally analysed are summarised by the arithmetic mean, standard deviation (SD), median, and minimum and maximum value. Endpoints that are analysed log-transformed are supplemented with the geometric mean and coefficient of variation. For measurements over time, mean values will be plotted to explore the trajectory over time. The geometric mean values will be plotted for

endpoints that are analysed log-transformed. All descriptive summaries and plots will be based on in-trial data unless otherwise specified.

If an assessment has been made both at screening and randomisation, and if not otherwise specified, the value from the randomisation visit will be used as the baseline value. If the value measured at the randomisation visit is missing and the assessment has also been made at screening, then the screening value will be used as the baseline value. For summaries and statistical analysis of all endpoints the first non-missing values is used. The value should be taken according to the specification in the protocol, e.g. non-fasting FPG-values are not used. Re-tests of non-missing values are only included in subject specific listings.

Laboratory values below the lower limit of quantification (LLOQ) will be set to $\frac{1}{2}\text{LLOQ}$.

Presentation of results from a statistical analysis will include the estimated mean treatment effects for absolute values and change from baseline. The estimated means are either obtained by Rubin's rule weighing together estimated means from multiple imputation or directly from estimation in a parameterized statistical model. In addition estimated mean treatment differences (or ratios) will be presented together with two-sided 95% confidence intervals and corresponding two-sided p-values.

2.1 Primary and secondary estimands

The primary estimand will be the difference in change from baseline at week 26 or week 38 depending on the endpoint considered between IDegAsp OD and IGlar OD + IAsp OD, for all randomised subjects regardless of whether the subjects remained on initially assigned treatment until week 26 or week 38. This estimand is a de facto estimand addressing effectiveness.

The secondary estimand will be the difference in change from baseline at week 26 or week 38 depending on the endpoint considered between IDegAsp OD and IGlar OD + IAsp OD if all randomised subjects had adhered to treatment until week 26 or week 38. This estimand is a de jure estimand addressing efficacy.

For hypoglycaemic episode endpoints, only the de jure estimand will be used. The reason for this is that data for hypoglycaemic episodes will not be systematically collected after treatment discontinuation.

